2.1 Background

2.1.1 Study Problem and Research Question

Recovery after surgery and anaesthesia has traditionally been assessed with objective measures including time to awakening, time to regaining airway reflexes, duration of stay in the recovery room and/or hospital, and incidence of adverse events like pain and post-operative nausea and vomiting. Increasingly, the patient's experience of their post-operative recovery is being recognised as an important outcome after surgery. The 15-Item Quality of Recovery score (QoR-15) has been validated to give a patient-centred global measure of overall health status after surgery and anaesthesia (1,2). This score has recently been translated and validated in isiZulu (3).

Desflurane is the newest anaesthetic vapour to market, with many benefits from the anaesthetist's perspective: faster time to awakening, faster time to regaining airway reflexes, and a clearer sensorium post-operatively. However, there is a paucity of data evaluating whether this translates to better quality of recovery for the patient. Desflurane is more expensive than other volatiles; for economic use, it is recommended to use Desflurane with a low flow (up to 2L) anaesthetic technique.

Isoflurane is the most commonly used volatile anaesthetic agent at [name] Academic Hospital. Concerns about the increased cost of desflurane compared to isoflurane limits the use of this novel agent in the public sector in South Africa. Following an extensive literature review, no studies could be found comparing quality of recovery between desflurane and isoflurane using a validated quality of recovery tool like the QoR-15.

The **research question** in this study is whether there is a clinically significant difference in post-operative quality of recovery (using the QoR-15 score) between desflurane and isoflurane inhalational anaesthesia in adult patients presenting for elective ophthalmological surgery under general anaesthesia.

This study will therefore compare quality of recovery between desflurane and isoflurane inhalational anaesthesia. Furthermore, the study will evaluate the relative cost of using either volatile with a minimal or basal flow anaesthetic technique.

2.1.2 Literature Review

The ideal volatile anaesthetic should be potent, with a low solubility in blood and tissues, which should promote fast onset and offset of the drug effect. It should provide safe, effective and reliable anaesthesia with minimal side-effects. The agent must be able to resist physical and metabolic degradation, and it should not pose a threat to the environment (4). Preferably, it should also be cost-effective and simple to use. One aspect that is often overlooked in the description of the "ideal anaesthetic agent", is the quality of recovery from the patient's point-of-view.

Isoflurane is the most commonly used inhaled anaesthetic agent at [name] Academic Hospital. Desflurane has recently become available. Both agents are indicated for maintenance of anaesthesia. Neither agent is indicated for induction of anaesthesia, as they are pungent and irritating to the airways.

The side-effect profiles of the two vapours are similar. Both agents may cause respiratory irritation (coughing, bronchospasm, laryngospasm) and respiratory depression. Both agents may cause myocardial depression and hypotension in a dose-dependent fashion. Desflurane may cause a transient, indirect stimulation of the sympathetic nervous system which may arise from stimulation of rapidly adapting upper airway receptors. Isoflurane may also cause emergence reactions, cardiac arrhythmias, involuntary muscle movements and

hiccupping. Both agents may cause post-operative shivering, nausea and vomiting, as well as leucocytosis (even in the absence of surgical stress). Both agents may interact with carbon dioxide adsorbents to form carbon monoxide, especially when the adsorbent dries out; carbon monoxide inhalation may lead to formation of carboxyhaemoglobin in exposed patients (5–7).

Both Isoflurane and Desflurane are contra-indicated in patients who may be susceptible to Malignant Hyperthermia or to auto-immune hepatitis. Isoflurane should be avoided in patients with cerebral space occupying lesions or raised intracranial pressure. Both agents will be contra-indicated when general anaesthesia is contra-indicated.

“Recovery” and “Quality of Recovery” are complex, abstract concepts, lacking in universally accepted definitions. In basic terms, “Recovery” can be seen as a return to the patient’s pre-operative state, or indeed, to an improved state. This is dependent on patient, surgical and anaesthetic factors. “Quality of Recovery” is a patient-centred concept, and several valid and reliable instruments have been developed that take into account physical and mental well-being factors that impact on the patient’s experience of their recovery (8).

Quality of recovery should be distinguished from patient satisfaction. Whether quality of recovery has an impact on patient satisfaction is unclear (9). Patient expectations, cultural and social background and cognitive factors all impact on patient satisfaction. Tools evaluating patient satisfaction emphasise the following: information provided to the patient, physical comfort, involvement in care, emotional support and privacy (8).

Recovery after inhaled anaesthesia has mostly been evaluated by parameters related to speed of emergence from anaesthesia, for example: time to open eyes, time to respond to command, time to remove LMA, and time to state date of birth. For all of these parameters, the time to effect is significantly shorter for desflurane compared to sevoflurane, isoflurane and propofol (4,10,11).

Some studies have evaluated later end-points of recovery including level of activity and side-effects on the day after surgery. Mahmoud et al (12) evaluated female patients who underwent laparoscopic gynaecological day-case surgery with either sevoflurane or desflurane for maintenance of anaesthesia; they found that the patients who received desflurane had greater return to normal activity the day after surgery compared to the sevoflurane group. This was done using a semi-structured telephonic questionnaire. White et al (13) found no difference in later end-points of recovery between sevoflurane and desflurane in patients undergoing superficial surgical procedures. This was assessed with a telephonic interview the day after surgery. This trial also included a basic assessment of patient satisfaction with their anaesthetic experience on a 3-point rating scale: 0 = dissatisfied, 1 = satisfied and 2 = highly satisfied. There was no difference in satisfaction between the two groups.

Studies comparing desflurane and isoflurane have been done, most also focussing on parameters relating to emergence from anaesthesia, as stated above. Emergence has been found to be faster for patients receiving desflurane; a finding that holds true for obese and elderly patients (4). Many of the early studies aimed for alveolar concentrations in excess of 1x the minimum alveolar concentration (MAC) of the volatile agents, which may explain the greater incidence of adverse reactions seen with desflurane. Jakobsson et al (14) compared desflurane and isoflurane anaesthesia in patients undergoing laparoscopic gynaecological surgery. Their study confirmed shorter time to emergence with desflurane, including time to extubation and return of cognitive function, and similar rates of post-operative nausea and vomiting and pain. Patients were asked to rate the quality of anaesthesia as "good – better than expected" or "bad – worse than expected". There was no significant difference between the two groups.

A systematic review published in 2004 comparing the recovery profiles after ambulatory anaesthesia with propofol, isoflurane, sevoflurane and desflurane, included 4 studies comparing desflurane and isoflurane. Unfortunately, none of the studies included in the review reported on later end-points of recovery or quality of recovery (15).

Few studies comparing volatile anaesthetic agents used validated quality of recovery tools. One study, reported in German in 2011, used the QoR-40 at 24 hours to evaluate differences between anaesthesia with desflurane and sevoflurane. Though parameters for early postanaesthetic recovery were superior in the patients receiving desflurane, there was no difference in the QoR-40 after 24 hours (16). A recently published randomised controlled trial primarily evaluating the effects of desflurane, sevoflurane and propofol on emergence times and airway reactions, evaluated patient responses to the Post-operative Quality of Recovery Score (PQRS) as a secondary outcome, and found no difference in quality of recovery between the groups (11).

Numerous tools have been developed in recent years to evaluate the quality of recovery from the patient's perspective (8). Multi-dimensional scales like the 24h Functional Ability Questionnaire (24h-FAQ), Postoperative Recovery Profile, Postoperative Quality of Recovery Scale (PQRS), Functional Recovery Index (FRI), and the 40-Item and 15-Item Quality of Recovery Scores (QoR-40 and QoR-15) have demonstrated comprehensive postoperative outcome results. The recent systematic review by the StEP-COMPAC group (Standardized Endpoints for Perioperative Medicine, Core Outcomes Measures in Perioperative and Anaesthetic Care) recommended one or more of six defined end-points be used in clinical trials assessing patient comfort after surgery (17). The QoR-15 is included in this list of six end-points: pain intensity at 24 h postoperatively, nausea and vomiting, one of two quality-of-recovery (QoR) scales (QoR score or QoR-15), time to gastrointestinal recovery, time to mobilisation, and sleep quality. The systematic review by Kleif et al (2) also recommends that the QoR-15 be used as a standard measure of quality of recovery in clinical trials in surgery and anaesthesia.

Previously, the QoR-40 was recommended as a global measure to assess the patient's experience of their overall health status after surgery and anaesthesia, but it takes around 10 minutes to complete. The QoR-15 was developed as an abbreviated version of the QoR-40, that would be more feasible in research and clinical practice; this questionnaire can be completed in less than 3 minutes (1).

The QoR-15 is a 15-item post-operative score evaluating both physical and mental well-being by assessing five dimensions: emotional state, physical comfort, psychological support, physical independence and pain. Each of the 15 items are scored by the patient from 0 (worst score) to 10 (best score), giving a lowest possible score of 0, and a highest possible score of 150. This continuous composite score allows comparisons between intervention groups. The minimal clinically important difference (MCID) and patient acceptable symptom state score for the QoR-15 score has been determined: the MCID is 8 and the acceptable symptom state score is 118 (18). The QoR-15 has good scaling properties, and during development and testing the scores followed a normal distribution (1).

The QoR-15 has undergone extensive validation and psychometric evaluation. The English and translated versions have been found to have good validity and reliability in assessing quality of recovery (2). During development and testing, the QoR-15 was able to discriminate between men and women. This is important as it has previously been shown that women generally have a worse post-operative experience. The QoR-15 furthermore showed a negative correlation with duration of surgery, duration of time spent in the post-anaesthesia care unit, and duration of hospital stay (1).

During an extensive review of the literature, no studies could be found comparing quality of recovery between desflurane and isoflurane using a validated quality of recovery tool like the QoR-15. Isoflurane is the most commonly used volatile anaesthetic agent at [name] Academic Hospital. Desflurane is being introduced into our practice, and it remains to be seen if it holds benefits with regards to patient-rated quality of recovery.

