1.1.2 WHO Data Set

Data category	Information
Primary registry and trial identifying number	ClinicalTrials.gov: NCT04188314
Date of registration in primary registry	4 December 2019
Secondary identifying numbers	SAHPRA Phase IV Notification: N20210205
Source(s) of monetary or material support	JPRF Research Fund
Primary sponsor	JPRF Research Fund
Secondary sponsor(s)	Abbvie Scholarship
Contact for public queries	[name]: [contact]
Contact for scientific queries	[name]: [contact]
Public title	Comparing Quality of Recovery Between Desflurane & Isoflurane in Eye Surgery Patients at [name] Academic Hospital (DIQoR Trial)
Scientific title	A Randomised Control Trial to Compare Quality of Recovery between Desflurane and Isoflurane Inhalational Anaesthesia in Patients Receiving General Anaesthesia for Ophthalmological Surgery at [name] Academic Hospital (DIQoR Trial)
Countries of recruitment	South Africa
Health condition(s) or problem(s) studied	Quality of Recovery after General Anaesthesia
Intervention(s)	Control drug: Isoflurane Intervention drug: Desflurane
Key inclusion and exclusion criteria	Ages eligible for study: 18-80 years Sexes eligible for study: both Accepts healthy volunteers: no Inclusion criteria: adult patients (18-80 years), patients presenting for ophthalmological surgery under general anaesthesia, ASA I and II, able to communicate in English, Setswana or Afrikaans.

Data category	Information
	Exclusion criteria: ASA III and above, contra-indications to Laryngeal Mask Airway use during general anaesthesia, severe medical or surgical conditions who are expected to have prolonged admissions or ICU admissions, uncontrolled psychiatric conditions, known allergy or adverse reaction to volatile anaesthetics, known or suspected susceptibility to Malignant Hyperthermia, incomplete records, patients who are not treated according to the prescribed treatment protocol.
Study type	Interventional Allocation: randomised Masking: double blind (patient and observer)
Date of first enrolment	February 2020
Target sample size	180
Recruitment status	Recruiting
Primary outcome(s)	To evaluate whether there is a difference between post-operative quality of recovery in patients who received desflurane and in patients who received isoflurane for maintenance of anaesthesia, using the QoR-15 score, a patient-rated outcome measure.

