3.2.2 Eligibility Criteria

Inclusion Criteria:

- Adult patients between the ages of 18-80 years of age.
- Patients presenting for ophthalmological surgery under general anaesthesia.
- ASA I and II.
- Able to communicate in English, Setswana or Afrikaans.

Exclusion Criteria:

- Patients outside the specified age range.
- ASA III and above.
- Patients with contra-indications to Laryngeal Mask Airway use during general anaesthesia.
- Patients with severe medical or surgical conditions, who are expected to have prolonged admissions or ICU admissions.
- Patients with uncontrolled psychiatric conditions like depression, schizophrenia, mania, dementia.
- Patients with known allergy or adverse reaction to volatile anaesthetics.
- Patients with known or suspected susceptibility to Malignant Hyperthermia.
- Patients with incomplete records (Data Collection Form and QoR-15).

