3.2.9 Recruitment

Recruitment will be done by the Chief Investigator. The following steps will be followed:

1. Review the theatre booking list for theatre 11 the day before surgery.
2. Identify adult patients between the ages of 18 and 80 on the list, scheduled for general anaesthesia.
3. Review the patients in the ward:
 - a. Screen for any exclusion criteria.
4. Once confirmed that there are no exclusion criteria:
 - a. Explain the objectives of the study to the patient.
 - b. Hand the patient a patient information leaflet and discuss any questions the patient may have.
 - c. Take informed consent if the patient agrees to participate in the study.
5. Record the patient's name on a sequentially numbered list. This will be the only document to contain any personal information of the patient. It will be stored securely by the Chief Researcher. The number on the list will be the patient's study number and this number will be recorded on all study documents.

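### Two of the three agent-specific warnings in section 2.1.2 are missing from the exclusion criteria (minor, patient safety)

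*Combined protocol and SAP*

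**What the plan says.** Section 2.1.2 sets out when the study agents should not be used. For both agents: "Both Isoflurane and Desflurane are contra-indicated in patients who may be susceptible to Malignant Hyperthermia or to auto-immune hepatitis". For the control agent alone: "Isoflurane should be avoided in patients with cerebral space occupying lesions or raised intracranial pressure".

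The exclusion list in 3.2.2 carries over one of these items: "Patients with known or suspected susceptibility to Malignant Hyperthermia". The registry list in 1.1.2 does the same ("known or suspected susceptibility to Malignant Hyperthermia, incomplete records"), and 3.7.3 repeats that exclusion. None of the three places names auto-immune hepatitis, an intracranial lesion or raised intracranial pressure.

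The nearest general exclusions in 3.2.2 are "Patients with known allergy or adverse reaction to volatile anaesthetics", ASA III and above, and "Patients with severe medical or surgical conditions, who are expected to have prolonged admissions or ICU admissions". Under 3.2.9 the Chief Investigator sees the patient on the ward the day before surgery with the instruction "Screen for any exclusion criteria". Explanation of the study and consent follow once none is found.

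**The concern.** One half of a single contra-indication sentence became an eligibility rule and the other half did not. The separate caution about isoflurane did not become one either. No section gives a reason. Someone who applied the written list exactly could enrol and randomise a patient who, by the protocol's own account, should receive neither agent (hepatitis susceptibility) or should not receive isoflurane (intracranial condition).

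What is at stake is patient safety. There is also a small practical consequence. The treating anaesthetist receives the sealed envelope on the day of surgery (3.3.1). If the problem is recognised only then, the choice is to give the allocated agent or to depart from the protocol. Section 3.2.3 describes no other maintenance agent, and the SPIRIT checklist in 6.1 marks the item on modifying an allocated intervention as not applicable. The registry list in 1.1.2 also excludes "patients who are not treated according to the prescribed treatment protocol", so correct clinical care would turn a foreseeable screening failure into an exclusion after randomisation.

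**Working it through.** No arithmetic in the plan bears on this point beyond a count, so the check is a comparison of sections.

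**Step 1. Match each agent-specific item in 2.1.2 to the exclusion lists.**

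| Item in 2.1.2 | Agent | Strength of wording | Named in 3.2.2 and 1.1.2? |
|---|---|---|---|
| Malignant hyperthermia susceptibility | both | contra-indicated | yes |
| Auto-immune hepatitis susceptibility | both | contra-indicated | no |
| Cerebral space-occupying lesion or raised intracranial pressure | isoflurane | to be avoided | no |

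Three items, one named: 3 − 1 = 2 not named. Section 2.1.2 also mentions contra-indications to general anaesthesia itself. That is not specific to an agent and is not at issue here.

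**Step 2. Ask whether another criterion covers the two unnamed items.**

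- *Known allergy or adverse reaction to volatiles.* This would catch a patient with an earlier volatile-related hepatitis. It needs a known reaction, whereas 2.1.2 speaks of patients who may be susceptible. The protocol's own treatment of malignant hyperthermia is informative: it has a separate line for known or suspected susceptibility beside the reaction line, so the reaction line was not taken to cover susceptibility there.
- *ASA III and above.* This probably removes most patients with a significant intracranial lesion, raised pressure or active liver disease. It does not name these conditions, so cover depends on the class assigned to each patient.
- *Severe conditions.* This applies only where prolonged or ICU admission is also expected, so a milder condition falls outside it.
- *Laryngeal mask contra-indications and uncontrolled psychiatric conditions.* Neither addresses these items.

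**Step 3. Ask whether the process covers them.** The day before surgery the Chief Researcher takes information from the file and from an interview (3.4.3). The file holds history, comorbidities and past anaesthetic complications (3.4.1). This may well bring either condition to light before allocation. It supplies the information, but no written rule says that such a patient is ineligible.

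**Step 4. Size.** The documents give no prevalence for either condition, so the number of affected patients cannot be calculated. Steps 2 and 3 suggest that it is very small.

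**The case against.** The strongest reply has four parts.

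*The screener is a clinician.* The Chief Researcher assisted treating anaesthetists at induction in the pilot and instructed colleagues in desflurane use (3.2.5). She reviews every patient before the envelope is opened, so the natural point of detection is before allocation. This stands, and it is the main reason the point is minor. A reader might infer that screening is confined to the listed criteria; 3.2.9 does not say that other contra-indications must be ignored.

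*The remaining group is not established.* The documents do not define the ASA classes, so whether a patient with an intracranial lesion can be ASA I or II is a clinical assumption. Possible susceptibility to hepatitis is also hard to apply without saying which history counts. Both remarks are fair. The first limits the intracranial part of the point; the second is a reason for clinical leads to settle the wording.

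*The data collection form.* A reader might infer a screening gap from Section A of the form in 6.7, which has no box for liver or intracranial disease. The documents do not support that inference. Section A has no box for malignant hyperthermia or volatile allergy either, and both are named exclusions. It records data and is not the eligibility screen, and its free-text comorbidity field could hold either history.

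*Timing.* The current version is dated 19 April 2021 (1.2) and data collection is planned to end in July 2021 (1.5). Few patients could benefit from a change made this late. That lowers the value of the amendment but does not make the lists consistent with 2.1.2.

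**Conclusion.** The gap in the written rules is real: the exclusion lists carry over one of three agent-specific items, and the general criteria narrow the gap without closing it. The point is minor, because the remaining group is probably very small and bedside judgement may still prevent exposure. Confidence is high for the mismatch in the text; nothing here estimates the chance of harm.

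Three stronger conclusions might be drawn, and the documents support none of them. The first is that contra-indicated patients will in fact be treated; the pre-operative review and the unblinded anaesthetist (3.3.2) stand in the way. The second is that an intracranial condition rules out both arms; 2.1.2 gives that caution for isoflurane only and says avoid, not contra-indicated. The third is that the primary comparison is biased or underpowered; nothing in the documents suggests this, and the sample size calculation in 3.2.8 is untouched.

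The verdict assumes that 2.1.2 states the authors' own clinical position, and that some patients with these conditions would be classed ASA I or II.

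**What to change.** Add two lines to the exclusion criteria in 3.2.2 and to the registry list in 1.1.2:

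- known or suspected susceptibility to auto-immune hepatitis;
- known cerebral space-occupying lesion or raised intracranial pressure.

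Apply both to every patient before randomisation, whichever arm may follow, at the existing file review and interview on the day before surgery. The intracranial line has to apply to all patients because the arm is not yet known at screening. Clinical leads should confirm the wording and state which history counts as suspected hepatitis susceptibility. The anaesthetists' leaflet in 6.6 needs no change: it does not reproduce the exclusion list.

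The cost is the amendment wording, one or two questions at a visit that already takes place, and notification of the SMU Research Committee and the SMU Research Ethics Committee, as section 4 requires for eligibility changes. A few patients may become ineligible. Section 3.2.1 counts 166 general anaesthetics from 1 March to 31 August 2018, which is 184 days. At that rate, replacing one patient takes at least 184/166 = 1.1 days, and longer to the extent that not all such patients are eligible and consent.
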